#### 10.1.2 SHORT-FORM QUESTIONNAIRE

The SF-36 is a widely used general health status questionnaire that assesses 8 domains of functional health and well-being: Physical Functioning, Role Limitations due to Physical Health Problems, Bodily Pain, Social Functioning, Mental Health, Role Limitations due to Emotional Problems, Vitality, and General Health Perceptions. Scales are scored from 0 to 100, with higher scores indicating a better health-related quality of life. A Physical Health component summary score and Mental Health component summary score are calculated from the 8 domain scores. The SF-36 is a psychometrically valid and reliable instrument. The concepts measured by the SF-36 are not specific to any age, disease, or treatment group, allowing comparison of relative burden of different diseases and the relative benefit of different treatments.

### 11 SUBGROUP ANALYSIS

No subgroup analysis is planned.

### 12 CONTINUED BLINDED TREATMENT AND OPEN-LABEL ANALYSIS

Any efficacy, safety, PK, and PD data assessments that are completed during safety follow-up, CBT and OL phase will be analyzed and summary tables will be provided.

Safety data will be analyzed based on the methods described in [Section 9](#) PK and PD data will be analyzed based on the methods described in [Section 7](#). Immunogenicity assessments outlined in [Section 7.2](#) may also be further analyzed during the CBT and OL phase. Efficacy endpoints that are assessed in the CBT and OL phase will be analyzed based on the methods described in [Section 6.2](#). All data for the CBT and OL phase will be summarized up until [CCI](#) or until subject's discontinuation from the study.

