6.4.2 Open-Label Phase

Subjects who are eligible to enter the OL phase as described in Section 3.1.2 will receive their first dose of PT101 (there is no Placebo treatment arm in the Open-Label Phase) on Day 85. [REDACTED] Assessments in this phase will mainly assess safety and exploratory efficacy. [REDACTED] Subjects will have a safety follow-up visit approximately 28 days after their last dose of study drug. They will also receive a follow-up call approximately 90 days after the final dose of PT101 to assess any changes in UC disease status. Subjects will be asked whether their UC is active, whether they have experienced a UC flare (defined as period of active symptoms), and whether they have started a new therapy for UC.

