### 4.2.1 INTENT-TO-TREAT ANALYSIS SET

The intent-to-treat analysis set (ITT) consists of all randomized subjects. Subjects will be included in the treatment group assigned at randomization regardless of the actual treatment received. All efficacy endpoints will be analyzed based on the ITT.

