#### 6.2.1.1 Statistical Methods for Dichotomous Efficacy Endpoints

The proportion of subjects achieving each of the dichotomous efficacy endpoints defined in [Table 5](#) will be summarized by treatment group using frequency distribution. To compare the proportion of subjects at a timepoint [CCI](#) the Cochran-Mantel-Haenszel (CMH) method will be used, and an exact 95% CI will be estimated. Missing values in the categorical endpoints will be imputed as non-responders. All dichotomous efficacy endpoints will be listed in by-subject listings.

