#### 6.2.2.1 Statistical Methods for Continuous Efficacy Endpoints

Continuous endpoints will be summarized by treatment group using descriptive statistics of the values at each visit and the change from baseline to each post-baseline visit. For continuous endpoints at only one post-baseline visit, an analysis-of-covariance (ANCOVA) will be used for analysis. The changes from baseline will be compared between treatments adjusted for the baseline value.

For continuous data with repeated measures post-randomization, mixed-model-repeated measure (MMRM) will be used for analysis. The model will include fixed effects for treatment, visit, baseline value, and treatment-by-visit interaction. This analysis will be conducted by maximum likelihood methods using the SAS PROC MIXED procedure. Least squares means and 95% CIs will be provided for each assessment timepoint.

All collected efficacy data will also be presented in a by-subject listing.

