#### 6.2.4 MISSING DATA HANDLING

##### 6.2.4.1 Non-responder Imputation

For the responder analyses described in [Table 5](#), subjects who do not have sufficient measurements to determine the endpoint will be considered as non-responders (i.e., non-responder imputation [NRI]). Specifically, all subjects who discontinue from the study at any time prior to the assessment timepoint or fail to have an adequate efficacy assessment at the timepoint will be considered a non-responder. The NRI may be applied at any time point specified for analysis.

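### SAP Section 12 carries the between-treatment model of Section 6.2 into the continued blinded and open-label phases, where it no longer gives a randomised comparison of PT101 with placebo

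*SAP*

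**What the plan says.** SAP Section 12 sets one rule for efficacy in both extension phases: "Efficacy endpoints that are assessed in the CBT and OL phase will be analyzed based on the methods described" in Section 6.2. It excludes no part of Section 6.2. It also gives no analysis set, treatment grouping or baseline of its own.

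Section 6.2 contains by-group summaries, and it also contains comparisons:

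- **Proportions (6.2.1.1):** "To compare the proportion of subjects at a timepoint", the Cochran-Mantel-Haenszel (CMH) method is used.
- **One post-baseline visit (6.2.2.1):** ANCOVA. "The changes from baseline will be compared between treatments adjusted for the baseline value".
- **Repeated visits (6.2.2.1):** MMRM. "The model will include fixed effects for treatment, visit, baseline value, and treatment-by-visit interaction".

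On the analysis set, SAP 4.2.1 says: "All efficacy endpoints will be analyzed based on the ITT". On grouping it says: "Subjects will be included in the treatment group assigned at randomization regardless of the actual treatment received".

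Protocol 3.1.2 decides who enters each phase. Week 12 clinical responders may enter CBT and keep their blinded allocation. Non-responders may choose OL, and Protocol 6.4.2 notes that "there is no Placebo treatment arm in the Open-Label Phase".

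The only efficacy endpoint listed beyond Week 12 is change from baseline in partial Mayo Score (Protocol 2.2.3; SAP Table 1, with the week redacted). Protocol 9.3.5 allows an MMRM to compare it.

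**The concern.** The Section 6.2 comparisons are built for the initial blinded phase, where the groups differ only by randomisation and the placebo group takes placebo. After Week 12 one of these conditions fails in each phase. In OL nobody takes placebo. In CBT the groups consist of subjects who responded, and response at Week 12 may itself depend on treatment.

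If the rule is followed as written, the tables will show a difference labelled PT101 against placebo, with a confidence interval, for quantities that do not measure that difference. A reader of the study report could take a small OL difference as lack of effect, or a CBT difference as evidence about maintained benefit.

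**Working it through.** The plan states no figure on this point, so there is none to reproduce. The check sets the rules side by side and then does the allocation arithmetic.

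**1. Which Section 6.2 method applies.** Partial Mayo change is continuous and measured repeatedly, so Section 6.2.2.1 assigns it to the MMRM. The SAP wording is firm (the model will be used), whereas Protocol 9.3.5 is permissive.

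**2. OL.** Under the ITT rule, a subject randomised to placebo stays in the placebo group while receiving OL PT101. Both columns are then PT101. The full analysis set (SAP 4.2.2) does not settle the matter, because grouping by actual treatment is ambiguous for someone who took placebo and then PT101. Baseline for partial Mayo Score is Day 1 (SAP 6.1.1.6), so change from baseline for these subjects also spans 12 weeks on placebo.

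**3. CBT.** The treatments still differ and remain blinded, but entry depends on a post-randomisation outcome. If PT101 raises the Week 12 response rate, placebo responders are a more favourably selected group than PT101 responders.

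**4. Numbers.** At 8:2 per cohort of 10 (Protocol synopsis, sample size), there are 3 x 2 = 6 placebo subjects in Cohorts 1-3 and 6 x 2 = 12 in six cohorts. Let p be the assumed placebo response at Week 12. The expected number of placebo responders is n x p, and the chance of none is (1 - p)^n.

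| p (assumed) | n = 6: expected | n = 6: chance of none | n = 12: expected | n = 12: chance of none |
|---|---|---|---|---|
| 10% | 0.6 | 53% | 1.2 | 28% |
| 20% | 1.2 | 26% | 2.4 | 7% |
| 30% | 1.8 | 12% | 3.6 | 1% |
| 40% | 2.4 | 5% | 4.8 | 0.2% |

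These figures suppose that every responder enters CBT, so the expected counts are upper limits. The former placebo subjects eligible for OL number n x (1 - p): 5.4 down to 3.6 of 6, or 10.8 down to 7.2 of 12.

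**5. Illustration of selection.** A simulation of 2,000,000 draws gave each subject a latent prognosis U. Week 12 response was U plus noise above a cut-off set to give the assumed rate in each arm. The later outcome was U plus fresh noise, with 40% responding overall and no treatment effect after Week 12.

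| Week 12 response, placebo / PT101 (assumed) | Later response in CBT, placebo vs PT101 | Later response in OL, former placebo vs former PT101 |
|---|---|---|
| 10% / 30% | 76% vs 64% | 36% vs 30% |
| 20% / 40% | 69% vs 60% | 33% vs 27% |
| 30% / 50% | 64% vs 56% | 30% vs 24% |

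The gaps, about 8 to 12 points in CBT and 6 in OL, come from selection alone. The outcome here is binary and the rates are assumed, so this shows mechanism and direction and does not predict the bias in partial Mayo change.

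**6. The conditional part.** The timepoints in SAP Tables 5 and 6 are redacted. If a binary or single-visit endpoint is also scheduled in CBT or OL, CMH or ANCOVA would have the same fault. Non-responder imputation (SAP 6.2.4.1) covers "all subjects who discontinue from the study at any time prior to the assessment timepoint" and also those without an adequate assessment at the timepoint. On the ITT set, that second limb could count a subject in CBT as an OL non-responder, and the reverse.

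**The case against.** The best defence is that the plan is descriptive throughout. SAP 4.1 says efficacy results will be presented with descriptive statistics, Section 12 itself speaks of summary tables, and Protocol 9.3.4 calls all analyses descriptive. This softens the problem without removing it. The same Protocol section prescribes CMH, ANCOVA and MMRM, and it lists partial Mayo change beyond Week 12 by dose level and placebo. SAP Section 9 rules out inferential testing for safety, but Sections 6 and 12 contain no such limit for efficacy.

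A second defence is that, since everyone in OL takes PT101, grouping by randomised arm already separates placebo-to-PT101 from PT101-to-PT101. That is correct. What remains wrong in OL is the placebo label and the treatment contrast.

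Third, an as-randomised analysis pooling both phases would keep the randomisation. It would compare two policies, one of which switches placebo non-responders to PT101, and it would not compare PT101 with placebo. Section 12 does not state this aim, and does not say whether the phases are pooled.

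Two stronger readings are tempting. A reader might infer that the SAP will run CMH and ANCOVA in these phases and will count subjects in the other phase as failures. The documents do not show this: the only listed post-Week 12 efficacy endpoint is partial Mayo change, to which non-responder imputation does not apply, and the relevant timepoints are redacted. A reader might also infer that the trial's conclusions are at risk. They are not. The primary endpoint is safety through Week 12, and Protocol 9.3.4 bases dose and regimen selection on Week 12 data.

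**Conclusion.** The point holds for change in partial Mayo Score after Week 12: a stated rule leads to an MMRM treatment contrast that is not a randomised estimate of drug effect in either phase. For binary and single-visit endpoints it holds only if such endpoints are scheduled in CBT or OL, which cannot be seen.

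The consequence is confined to exploratory endpoints. The CBT placebo group is small across the assumed 10-40% response range, at most 2.4 expected of 6 or 4.8 of 12, but that range is an assumption. The selection bias in CBT further supposes that treatment affects Week 12 response. The OL labelling fault needs no assumption beyond at least one former placebo subject entering OL. A display of CBT by arm remains legitimate, since allocation and blinding are kept there; the fault lies in presenting it as a randomised contrast.

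**What to change.** Amend SAP Section 12 to state that:

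- CBT and OL efficacy are reported separately and descriptively, with no CMH, ANCOVA or MMRM treatment contrasts;
- the denominator in each phase is the subjects who entered it, so imputation cannot reach subjects in the other phase;
- OL results are shown by sequence, PT101 to PT101 and placebo to PT101;
- change is from the protocol's baseline, with change from the Week 12 phase-entry value as an optional addition for OL.

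The cost is a short paragraph and less modelling; the optional OL summary is the only added output. Because Protocol 9.3.5 only permits the MMRM, and Protocol Section 9 requires an amendment only where site conduct changes, the protocol can stay as it is. If the database is already locked, SAP 1.1 requires the change and its reason to be recorded in the clinical study report.

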### 13 DRC REVIEW

For the planning of dose-escalation, opening of an optional cohort, continuing the study without changes, modifying the study, and/or dose/regimen selection, a review of safety, PK, PD, and efficacy data will be performed by an external DRC throughout the course of the study as described in detail in the DRC Charter.

Progression from Cohort 1 to Cohort 2 per protocol will be based on DRC recommendations from all available unblinded safety, PK, and PD data reviewed from Cohort 1 along with all available unblinded safety data (all 10 subjects [PT101: placebo 4:1] up to [CCI](#)

[CCI](#) in a concurrent PT101 study conducted in young adult healthy volunteers population (MK-6194-003). Dose escalation from Cohort 2 to Cohort 3 will be determined only after the [CCI](#) in [CCI](#) reach [CCI](#)

[CCI](#) Up to 3 optional cohorts may be added following DRC review of all available data from the previous planned cohorts (Cohorts 1 to 3) to (a) assess additional dose levels of PT101 [CCI](#) dosing regimen, and/or (b) repeat a previously studied dose level/dosing regimen.

At each DRC meeting, the committee will review cumulative AE and safety data, as well as available PK, PD, UC disease activity, and biomarker data from all treated patients. The analysis will be presented blinded for the open sessions and unblinded for the closed sessions. The study may be stopped at the discretion of the sponsor based on recommendations of the DRC. All necessary measures will be taken to ensure appropriate safety follow-up for all subjects in the trial.

The following analysis may be provided:

- Section 5.1: Disposition and Subject Characteristics
- Section 5.3: Demographic and baseline characteristics
- Section 6.2.1: Dichotomous Efficacy Endpoints; clinical remission, clinical response, symptomatic remission, symptomatic response, endoscopic improvement, endoscopic remission, mucosal healing, histologic remission, histologic response.
- Section 6.2.2: Continuous Efficacy Endpoints; MCS, pMCS, mMCS, RHI, UC-100.
- Section 7.1: Pharmacokinetic Assessments: Descriptive statistics for available PK data
- Section 7.2/7.3: Pharmacodynamic Assessments: Descriptive statistics for available PD data
- Section 8: Biomarker Analyses: Descriptive statistics for available biomarker data
- Section 9: Safety Analyses: Overall summary of TEAEs, TEAEs by SOC and PT, TEAEs by SOC, PT and maximum severity, severe (CTCAE Grade  $\geq 3$ ) TEAEs by SOC and PT, Related TEAEs by SOC and PT, TESAEs by SOC and PT, descriptive statistics for ECGs, vital signs, clinical laboratory parameters.
- Section 13.1: Assessment of Dose-Limiting Toxicity: Overall listing of dose-limiting toxicity (DLT) AE's.

### 13.1 ASSESSMENT OF DOSE-LIMITING TOXICITY

A dose-limiting toxicity (DLT) is defined as any treatment-related AE reported within CCI from dosing that meets both the following criteria:

[figure not shown]
- Grade 3 or higher in severity according to the NCI CTCAE, Version 5.0
- A shift of  $\geq 2$  NCI CTCAE grades from baseline (initial presentation of the AE)

The safety of each dose level will be evaluated by examining the probability of experiencing a DLT based on a Bayesian Logistic Regression Model (BLRM) (Neuenschwander, 2008) and the incidence of TEAEs, TESAEs, treatment-related TEAEs, and treatment-related TESAEs.

A dose will be considered safe if the estimated probability (posterior median) of overdosing CCI The maximum tolerated dose (MTD) will be determined according to the following rules:

CCI

CCI

To support the dose selection decision, results from dose toxicity modeling using a 2-parameter BLRM will also be considered. The model parameters ( $\log(f_0/\alpha), \log(f_0/\beta)$ ) are given a weakly informative bivariate normal prior distribution, with prior means (-1.912, 0.167), prior standard deviations (2.424, 1.139), and prior correlation of 0.486. The target probability of toxicity is under 10% [Neuenschwander et al, 2014].

For Cohort 1, the model will be run using all available safety data from subjects that have completed

CCI

CCI

and subsequently at the same timepoint for the 3 potential optional cohorts. The analysis will be performed (using appropriate software, such as East Software [Cytel Inc, v6.4]) based on estimation of the posterior median. The selected dose may not exceed the escalation with overdose control (EWOC) threshold: the posterior probability of overdosing is 0.25. The dose level(s) and dosing regimen with the best benefit/risk profile based on the totality of safety and efficacy data at

CCI

will inform selection for future clinical development.

## 14 CHANGES FROM PROTOCOL

- Last observation carried forward (LOCF) was dropped from the SAP as an MMRM analysis planned and LOCF would not be efficient in this case.
- Protocol stated that the SAP would be finalized prior to the DRC review of Cohort 1 data, but the SAP will not be finalized until prior to the final database lock.
- Physical exam findings will only be included in a by-subject listing and no change from baseline calculations will be done..
- Removed receptor occupancy (RO) as a secondary objective along with corresponding analysis. Upon thorough investigation of the assay and data generated on production samples, technical issues related to the assay remained unresolved resulting in failure to obtain acceptable quality data and deeming the RO assay an assay failure for MK-6194-002. The assay main concerns were loss of CD4 resolution in the majority of production samples, lack of dynamic range between background and maximal MK-6194 signal to accurately calculate RO, and lack of true MK-6194 and Ki-67 production sample gating controls resulting in variable/subjective gate placement and erroneous data.

## 15 REVISION HISTORY

Version	Effective Date	Reason
V01	06DEC2022	New
V02	23FEB2024	Updated FAS definition and removed analysis related to receptor occupancy. Added additional biomarkers to the analyses in Section 8.

CCI

CCI

[figure not shown]

CCI

CCI

CCI

CCI

CCI

CCI

## APPENDIX B: MAYO SCORE

Note: The partial MCS is calculated using only the stool frequency, rectal bleeding, and physician's global assessment subscores from the table below.

Component	Mayo Score (MCS)
Stool Frequencya, d	
Normal number of stools for this subject	0
1 to 2 stools more than normal	1
3 to 4 stools more than normal	2
5 or more stools than normal	3
Subscore, 0 to 3	
Rectal bleedingb, d	
No blood seen	0
Streaks of blood with stool less than half the time	1
Obvious blood (more than just streaks) or streaks of blood with stool most of the time	2
Blood alone passes	3
Subscore, 0 to 3	
Findings on endoscopy	
Normal or inactive disease	0
Mild disease (erythema, decreased vascular pattern, no friability)	1
Moderate disease (marked erythema, absent vascular pattern, friability, erosions)	2
Severe (spontaneous bleeding, ulceration)	3
Subscore, 0 to 3	
Physician's global assessmentc	
Normal	0
Mild disease	1
Moderate disease	2
Severe disease	3
Subscore, 0 to 3	
Total score	0-12
a Each subject serves as his or her own control to establish the degree of abnormality of the stool frequency	

- b The daily bleeding score represents the most severe bleeding of the day
- c The physician's global assessment acknowledges the 3 other criteria, the subject's recollection of abdominal discomfort and general sense of wellbeing, and other observations, such as physical findings and the subject's performance status
- d The modified Mayo score calculated at the **CC1** visits must use the SF and RB Mayo subscores recorded on the eDiary (or paper diary) over the **3 consecutive days prior to the endoscopy** (excluding the bowel preparation day)

## APPENDIX C: GEBOES SCORING

Grade 0	Structural (architectural change)
Subgrades	
0.0	No abnormality
0.1	Mild abnormality
0.2	Mild or moderate diffuse or multifocal abnormalities
0.3	Severe diffuse or multifocal abnormalities
Grade 1	Chronic inflammatory infiltrate
Subgrades	
1.0	No increase
1.1	Mild but unequivocal increase
1.2	Moderate increase
1.3	Marked increase
Grade 2	Lamina propria eosinophils and neutrophils
2A Eosinophils	
2A.0	No increase
2A.1	Mild but unequivocal increase
2A.2	Moderate increase
2A.3	Marked increase
2B Neutrophils	
2B.0	None
2B.1	Mild but unequivocal increase
2B.2	Moderate increase
2B.3	Marked increase
Grade 3	Neutrophils in epithelium
3.0	None
3.1	< 5% crypts involved
3.2	< 50% crypts involved
3.3	> 50% crypts involved
Grade 4	Crypt destruction
4.0	None
4.1	Probable – local excess of neutrophils in part of crypt
4.2	Probable – marked attenuation

4.3	Unequivocal crypt destruction
Grade 5	Chronic inflammatory infiltrate
5.0	No erosion, ulceration, or granulation of tissue
5.1	Recovering epithelium + adjacent inflammation
5.2	Probable erosion – focally stripped
5.3	Unequivocal erosion
5.4	Ulcer or granulation tissue

## APPENDIX D: ROBARTS HISTOPATHOLOGY INDEX SCORING

Histological Variable	Grading	Multiplication Factor
Chronic inflammatory infiltrate	0=No increase 1=Mild but unequivocal increase 2=Moderate increase 3=Marked increase	X1
Lamina propria neutrophils	0=None 1=Mild but unequivocal increase 2=Moderate increase 3=Marked increase	X2
Neutrophils in epithelium	0=None 1=< 5% crypts involved 2=< 50% crypts involved 3=> 50% crypts involved	X3
Erosion or ulceration	0=No erosion, ulceration, or granulation tissue 1=Recovering epithelium + adjacent inflammation 1=Probably erosion-focally stripped 2=Unequivocal erosion 3=Ulcer or granulation tissue	X5

## APPENDIX E: QUALITY OF LIFE IN INFLAMMATORY BOWEL DISEASE QUESTIONNAIRE (IBDQ)

### INSTRUCTIONS FOR SELF-ADMINISTERED IBDQ

This questionnaire is designed to measure the effects of your inflammatory bowel disease on your daily function and quality of life. You will be asked about symptoms you have been having as a result of your bowel disease, the way you have been feeling in general, and how your mood has been.

There are two versions of this questionnaire, the IBDQ and IBDQ-Stoma. If you have a colostomy or ileostomy, you should complete the IBDQ-Stoma. Questions 1, 5, 17, 22, 24 and 26 are slightly different in each version. Be sure you have the correct questionnaire.

On this questionnaire there are 32 questions. Each question has a graded response numbered from 1 through 7. Please read each question carefully and circle/mark the number which best describes how you have been feeling in the past 2 weeks.

